#### 6.2.4.3 Disease Progression & Progression-Free Survival

PFS is defined as the duration of time from start of treatment to time of progression or death, whichever occurs first. The duration of progression-free survival is measured from the start of vicineum therapy until progression or death due to any cause. Disease progression is defined as upstaging from a lower stage to a higher stage (e.g., Ta to T1-T4 or T1 to T2-4; CIS to T1 or CIS to T2-T4; or any N+ or M+ in these high grade tumors).

#### 6.2.4.4 Time to Tumor Recurrence

The duration of time measured from the start of Vicineum therapy until recurrence is noted.

### 6.3 TOXICITY CRITERIA

The following adverse event management guidelines are intended to ensure the safety of each patient while on the study. The descriptions and grading scales found in the revised NCI Common Terminology Criteria for Adverse Events (CTCAE) version 5.0 will be utilized for AE reporting. All appropriate treatment areas should have access to a copy of the CTCAE version 5.0. A copy of the CTCAE version 5.0 can be downloaded from the CTEP web site ([http://ctep.cancer.gov/protocolDevelopment/electronic\\_applications/ctc.htm#ctc\\_50](http://ctep.cancer.gov/protocolDevelopment/electronic_applications/ctc.htm#ctc_50)).

## 7 NIH REPORTING REQUIREMENTS/DATA AND SAFETY MONITORING PLAN

### 7.1 DEFINITIONS

Please refer to definitions provided in Policy 801: Reporting Research Events found at: <https://irbo.nih.gov/confluence/pages/viewpage.action?pageId=36241835#Policies&Guidance-800Series-ComplianceandResearchEventReportingRequirements>.

### 7.2 OHSRP OFFICE OF COMPLIANCE AND TRAINING/IRB REPORTING

#### 7.2.1 Expedited Reporting

Please refer to the reporting requirements in Policy 801: Reporting Research Events and Policy 802 Non-Compliance Human Subjects Research found at:

<https://irbo.nih.gov/confluence/pages/viewpage.action?pageId=36241835#Policies&Guidance-800Series-ComplianceandResearchEventReportingRequirements>.

Note: Only IND Safety Reports that meet the definition of an unanticipated problem will need to be reported per these policies.

#### 7.2.2 IRB Requirements for PI Reporting at Continuing Review

Please refer to the reporting requirements in Policy 801: Reporting Research Events found at:

<https://irbo.nih.gov/confluence/pages/viewpage.action?pageId=36241835#Policies&Guidance-800Series-ComplianceandResearchEventReportingRequirements>.

### 7.3 NCI CLINICAL DIRECTOR REPORTING

Problems expeditiously reviewed by the OHSRP in the NIH eIRB system will also be reported to the NCI Clinical Director/designee; therefore, a separate submission for these reports is not necessary.

In addition to those reports, all deaths that occur within 30 days after receiving a research intervention should be reported via email unless they are due to progressive disease.

To report these deaths, please send an email describing the circumstances of the death to [[contact]](mailto:[contact]) within one business day of learning of the death.

## **7.4 NIH REQUIRED DATA AND SAFETY MONITORING PLAN**

### **7.4.1 Principal Investigator/Research Team**

The clinical research team will meet on a regular weekly basis when patients are being actively treated on the trial to discuss each patient. Decisions about dose level enrollment and dose escalation if applicable will be made based on the toxicity data from prior patients.

All data will be collected in a timely manner and reviewed by the principal investigator or a lead associate investigator. Events meeting requirements for expedited reporting as described in section **7.2.1** will be submitted within the appropriate timelines.

The principal investigator will review adverse event and response data on each patient to ensure safety and data accuracy. The principal investigator will personally conduct or supervise the investigation and provide appropriate delegation of responsibilities to other members of the research staff.

## **8 SPONSOR SAFETY REPORTING**

### **8.1 DEFINITIONS**

#### **8.1.1 Adverse Event**

Any untoward medical occurrence in a patient or clinical investigation subject administered a pharmaceutical product and which does not necessarily have a causal relationship with this treatment. An adverse event (AE) can therefore be any unfavorable and unintended sign (including an abnormal laboratory finding), symptom, or disease temporally associated with the use of a medicinal (investigational) product, whether or not related to the medicinal (investigational) product (ICH E6 (R2)).

#### **8.1.2 Serious Adverse Event (SAE)**

An adverse event or suspected adverse reaction is considered serious if in the view of the investigator or the sponsor, it results in any of the following:

- Death,
- A life-threatening adverse event (see **8.1.3**)
- Inpatient hospitalization or prolongation of existing hospitalization
  - A hospitalization/admission that is pre-planned (i.e., elective or scheduled surgery arranged prior to the start of the study), a planned hospitalization for pre-existing condition, or a procedure required by the protocol, without a serious deterioration in health, is not considered a serious adverse event.

- A hospitalization/admission that is solely driven by non-medical reasons (e.g., hospitalization for patient or subject convenience) is not considered a serious adverse event.
- Emergency room visits or stays in observation units that do not result in admission to the hospital would not be considered a serious adverse event. The reason for seeking medical care should be evaluated for meeting one of the other serious criteria.
- Persistent or significant incapacity or substantial disruption of the ability to conduct normal life functions
- A congenital anomaly/birth defect.
- Important medical events that may not result in death, be life-threatening, or require hospitalization may be considered a serious adverse drug experience when, based upon appropriate medical judgment, they may jeopardize the patient or subject and may require medical or surgical intervention to prevent one of the outcomes listed in this definition.

### **8.1.3 Life-threatening**

An adverse event or suspected adverse reaction is considered "life-threatening" if, in the view of either the investigator or sponsor, its occurrence places the patient or subject at immediate risk of death. It does not include an adverse event or suspected adverse reaction that, had it occurred in a more severe form, might have caused death. (21CFR312.32).

### **8.1.4 Severity**

The severity of each Adverse Event will be assessed utilizing the CTCAE version 5.0.

### **8.1.5 Relationship to Study Product**

All AEs will have their relationship to study product assessed using the terms: related or not related.

- Related – There is a reasonable possibility that the study product caused the adverse event. Reasonable possibility means that there is evidence to suggest a causal relationship between the study product and the adverse event.
- Not Related – There is not a reasonable possibility that the administration of the study product caused the event.

### **8.1.6 Adverse Events of Special Interest (AESI)**

An adverse event of special interest (AESI) is one of scientific and medical interest specific to understanding of the Investigational Product and may require close monitoring and rapid communication by the investigator to the sponsor. An AESI may be serious or non-serious. The rapid reporting of AESIs allows ongoing surveillance of these events in order to characterize and understand them in association with the use of this investigational product.

AESIs for durvalumab include but are not limited to events with a potential inflammatory or immune-mediated mechanism and which may require more frequent monitoring and/or interventions such as steroids, immunosuppressants and/or hormone replacement therapy. These AESIs are being closely monitored in clinical studies with durvalumab monotherapy and combination therapy. An immune-mediated adverse event (imAE) is defined as an AESI that is

associated with drug exposure and is consistent with an immune-mediated mechanism of action and where there is no clear alternate etiology. Serologic, immunologic, and histologic (biopsy) data, as appropriate, should be used to support an imAE diagnosis. Appropriate efforts should be made to rule out neoplastic, infectious, metabolic, toxin, or other etiologic causes of the imAE.

In the event of imAE or suspected imAE, the AstraZeneca study team may request relevant clinical information (including images) for those subjects who demonstrate the event, and may request the independent review by external experts based on the acquired clinical information.

AESIs observed with durvalumab include:

- Diarrhea / Colitis and intestinal perforation
- Pneumonitis / ILD
- hepatitis / transaminase increases
- Endocrinopathies (i.e. events of hypophysitis/hypopituitarism, adrenal insufficiency, hyper- and hypothyroidism and type I diabetes mellitus)
- Rash / Dermatitis
- Nephritis / Blood creatinine increases
- Pancreatitis / serum lipase and amylase increases
- Myositis / Polymyositis
- Neuropathy / neuromuscular toxicity (e.g. Guillain-Barré, and myasthenia gravis)
- Intestinal Perforations

Other inflammatory responses that are rare/less frequent with a potential immune-mediated etiology include, but are not limited to:

- Myocarditis
- Pericarditis
- Sarcoidosis
- Uveitis
- Other events involving the eye and skin
- Hematological events
- Rheumatological events
- Vasculitis
- Non-infectious meningitis
- Non-infectious encephalitis
- Pemphigoid

It is possible that events with an inflammatory or immune mediated mechanism could occur in nearly all organs. In addition, infusion-related reactions and hypersensitivity/anaphylactic reactions with a different underlying pharmacological aetiology are also considered AESIs.

Further information on these risks (e.g., presenting symptoms) can be found in the current version of the durvalumab Investigator's Brochure. More specific guidelines for their evaluation and treatment are described in detail in the Dosing Modification and Toxicity Management Guidelines (see [Appendix C](#)). These guidelines have been prepared by the Sponsor to assist the Investigator in the exercise of his/her clinical judgment in treating these types of toxicities. These guidelines apply to AEs considered causally related to the study drug/study regimen by the reporting investigator.

## **8.2 ASSESSMENT OF SAFETY EVENTS**

AE information collected will include event description, date of onset, assessment of severity and relationship to study product and alternate etiology (if not related to study product), date of resolution of the event, seriousness and outcome. The assessment of severity and relationship to the study product will be done only by those with the training and authority to make a diagnosis and listed on the Form FDA 1572 as the site principal investigator or sub-investigator. AEs occurring during the collection and reporting period will be documented appropriately regardless of relationship. AEs will be followed through resolution.

SAEs will be:

- Assessed for severity and relationship to study product and alternate etiology (if not related to study product) by a licensed study physician listed on the Form FDA 1572 as the site principal investigator or sub-investigator.
- Recorded on the appropriate SAE report form, the medical record and captured in the clinical database.
- Followed through resolution by a licensed study physician listed on the Form FDA 1572 as the site principal investigator or sub-investigator.

For timeframe of recording adverse events, please refer to section [6.1](#). All serious adverse events recorded from the time of first investigational product administration must be reported to the sponsor.

## **8.3 REPORTING OF SERIOUS ADVERSE EVENTS**

Any AE that meets a protocol-defined serious criteria or meets the definition of Adverse Event of Special Interest that require expedited reporting must be submitted immediately (within 24 hours of awareness) to OSRO Safety using the CCR SAE report form.

All SAE reporting must include the elements described in [8.2](#).

SAE reports will be submitted to the Center for Cancer Research (CCR) at:

[[contact]](mailto:[contact]) and to the CCR PI and study coordinator. CCR SAE report form and instructions can be found at: <https://nih.sharepoint.com/:u/r/sites/NCI-CCR-OCD-Communications/SitePages/Forms-and-Instructions.aspx?csf=1&web=1&e=uWBXtI>

Following the assessment of the SAE by OSRO, other supporting documentation of the event may be requested by the OSRO Safety and should be provided as soon as possible.

## **8.4 SAFETY REPORTING CRITERIA TO THE PHARMACEUTICAL COLLABORATORS**

### **8.4.1 Safety Reporting Criteria to AstraZeneca**

#### **8.4.1.1 Safety Reports sent by OSRO**

All SAEs will be reported, whether or not considered causally related to the investigational product, or to the study procedure(s). The reporting period for SAEs is the period immediately following the time that written informed consent is obtained through 90 days after the last dose of durvalumab or until the initiation of alternative anticancer therapy. The investigator and/or Sponsor are responsible for informing the Ethics Committee and/or the Regulatory Authority of the SAE as per local requirements.

The investigator and/or sponsor must inform the FDA, via a MedWatch/AdEERs form, of any serious or unexpected adverse events that occur in accordance with the reporting obligations of 21 CFR 312.32, and will concurrently forward all such reports to AstraZeneca. A copy of the MedWatch/AdEERs report must be emailed to AstraZeneca at the time the event is reported to the FDA. It is the responsibility of the sponsor to compile all necessary information and ensure that the FDA receives a report according to the FDA reporting requirement timelines and to ensure that these reports are also submitted to AstraZeneca at the same time.

\* A cover page should accompany the MedWatch/AdEERs form indicating the following:

- “Notification from an Investigator Sponsored Study”
- The investigator IND number assigned by the FDA
- The investigator’s name and address
- The trial name/title and AstraZeneca ISS reference number (ESR-##-#####)

\* Sponsor must also indicate, either in the SAE report or the cover page, the causality of events in relation to all study medications and if the SAE is related to disease progression, as determined by the principal investigator.

\* Send SAE report and accompanying cover page by way of email to AstraZeneca’s designated mailbox: [[contact]](mailto:[contact])

If a non-serious AE becomes serious, this and other relevant follow-up information must also be provided to AstraZeneca and the FDA.

#### **8.4.1.2 Safety Reports sent by the Study Team**

Serious adverse events that do not require expedited reporting to the FDA still need to be reported to AstraZeneca preferably using the MedDRA coding language for serious adverse events. This information should be reported on a monthly basis and under no circumstance less frequently than quarterly.

In the case of blinded trials, AstraZeneca will request that the Sponsor either provide a copy of the randomization code/ code break information or unblind those SAEs which require expedited reporting.

On a monthly basis, non-expedited SAEs will be provided to Collaborator Patient Safety Department via fax at: [contact] and email to: [[contact]](mailto:[contact]) and [[contact]](mailto:[contact]).

#### **8.4.2 Safety Reporting Criteria to Sesen Biotherapeutics**

As soon as the investigator becomes aware that an adverse event meets the criteria for being a serious adverse event (SAE) the following is required:

- The investigator will notify Sesen Biotherapeutics within twenty-four (24) hours of becoming aware of the SAE by submitting a completed SAE form and any supporting documentation to Sesen Biotherapeutics.
- The SAE form and supporting documentation should be scanned and emailed to Sesen Biotherapeutics at with [[contact]](mailto:[contact]) and [[contact]](mailto:[contact]).
- Follow-up information must be submitted in a timely fashion

All suspected unexpected serious adverse reactions (SUSARs), also called serious and unexpected suspected adverse reaction (i.e., serious, unexpected and related SAEs), must be reported to all appropriate regulatory authorities and IRBs/Ethics Committees as required by 21 CFR 312.32 utilizing the MedWatch 3500A form or the CIOMS-1. The final forms for the initial and all follow-up reports must be submitted within two (2) business days of submission to the FDA or other health authorities. These reports should be scanned and emailed to Sesen Biotherapeutics at [[contact]](mailto:[contact]) and [[contact]](mailto:[contact]).

### **8.5 REPORTING PREGNANCY**

All required pregnancy reports/follow-up to OSRO will be submitted to: [[contact]](mailto:[contact]) and to the CCR PI and study coordinator. Forms and instructions can be found here: <https://nih.sharepoint.com/:u/r/sites/NCI-CCR-OCD-Communications/SitePages/Forms-and-Instructions.aspx?csf=1&web=1&e=uWBXtI>

#### **8.5.1 Maternal exposure**

If a patient becomes pregnant during the course of the study, the study treatment should be discontinued immediately, and the pregnancy reported to the Sponsor no later than 24 hours of when the Investigator becomes aware of it. The Investigator should notify the Sponsor no later than 24 hours of when the outcome of the Pregnancy become known,

Pregnancy itself is not regarded as an SAE. However, congenital abnormalities or birth defects and spontaneous miscarriages that meet serious criteria (section **8.1.2**) should be reported as SAEs.

The outcome of all pregnancies should be followed up and documented.

#### **8.5.2 Paternal exposure**

Male patients should refrain from fathering a child or donating sperm during the study and for 120 days after the last dose of Durvalumab and Vicineum.

Pregnancy of the patient's partner is not considered to be an AE. The outcome of all pregnancies occurring from the date of the first dose until 120 days after the last dose should, if possible, be

followed up and documented. Pregnant partners may be offered the opportunity to participate in an institutional pregnancy registry protocol (e.g., the NIH IRP pregnancy registry study) to provide data about the outcome of the pregnancy for safety reporting purposes.

## **8.6 REGULATORY REPORTING FOR STUDIES CONDUCTED UNDER CCR-SPONSORED IND**

Following notification from the investigator, CCR, the IND sponsor, will report any suspected adverse reaction that is both serious and unexpected. CCR will report an AE as a suspected adverse reaction only if there is evidence to suggest a causal relationship between the study product and the adverse event. CCR will notify FDA and all participating investigators (i.e., all investigators to whom the sponsor is providing drug under its INDs or under any investigator's IND) in an IND safety report of potential serious risks from clinical trials or any other source, as soon as possible, in accordance to 21 CFR Part 312.32.

All serious events will be reported to the FDA at least annually in a summary format.

## **8.7 SPONSOR PROTOCOL DEVIATION REPORTING**

A Protocol Deviation is defined as any non-compliance with the clinical trial Protocol, Manual of Operational Procedures (MOP) and other Sponsor approved study related documents, GCP, or protocol-specific procedural requirements on the part of the participant, the Investigator, or the study site staff inclusive of site personnel performing procedures or providing services in support of the clinical trial.

It is the responsibility of the study Staff to document any protocol deviation identified by the Staff or the site Monitor in the CCR Protocol Deviation Tracking System (PDTs) online application. The entries into the PDTs online application should be timely, complete, and maintained per CCR PDTs user requirements.

In addition, any deviation to the protocol should be documented in the participant's source records and reported to the reviewing IRB per their guidelines. OSRO required protocol deviation reporting is consistent with E6(R2) GCP: Integrated Addendum to ICH E6(R1): 4.5 Compliance with Protocol; 5.18.3 (a), and 5.20 Noncompliance; and ICH E3 16.2.2 Protocol deviations.

## **9 CLINICAL MONITORING PLAN**

Clinical site monitoring is conducted to ensure:

- that the rights of the participants are protected;
- that the study is implemented per the approved protocol, Good Clinical Practice and standard operating procedures; and,
- the quality and integrity of study data and data collection methods are maintained.

Monitoring for this study will be performed by NCI CCR Office of Sponsor and Regulatory Oversight (OSRO) Sponsor and Regulatory Oversight Support (SROS) Services contractor. Clinical site monitoring activities will be based on OSRO standards, FDA Guidance E6(R2) Good Clinical Practice: Integrated Addendum to ICH E6(R1) March 2018, and applicable regulatory requirements.

Details of clinical site monitoring will be documented in a Clinical Monitoring Plan (CMP) developed by OSRO. CMPs will be protocol-specific, risk-based and tailored to address human subject protections and integrity of the study data. OSRO will determine the intensity and frequency of monitoring based on several factors, including study type, phase, risk, complexity, expected enrollment rate, and any unique attributes of the study and the site. The Sponsor will conduct a periodic review of the CMP to confirm the plan's continued appropriateness. A change to the protocol, significant or pervasive non-compliance with GCP, or the protocol may trigger CMP updates.

OSRO SROS Monitoring visits and related activities will be conducted throughout the life cycle of each protocol. The first activity is before the study starts to conduct a Site Assessment Visit (SAV) (as warranted), followed by a Site Initiation Visit (SIV), Interim Monitoring Visit(s) (IMVs), and a study Close-Out Visit (COV).

Some monitoring activities may be performed remotely, while others will occur at the study site(s). Monitoring visit reports will describe visit activities, observations, and associated action items or follow-up required for resolution of any issues, discrepancies, or deviations. Monitoring reports will be distributed to the study PI, NCI CCR QA, CCR Protocol Support Office, coordinating center (if applicable), and the Sponsor regulatory file.

The site Monitor will inform the study team of any deviations observed during monitoring visits. If unresolved, the Monitor will request that the site Staff enter the deviations in the CCR Protocol Deviation Tracking System (PDTs) for deviation reporting to the Sponsor and as applicable per institutional and IRB guidance.

## 10 STATISTICAL CONSIDERATIONS

### 10.1 STATISTICAL HYPOTHESES

#### **Primary endpoints:**

The primary objective of this trial is to determine whether the use of a combination of Vicineum and durvalumab in patients with high grade NMIBC previously treated with BCG is safe and tolerable as determined by a 3+3 dose de-escalation trial design. The primary endpoint will be the fraction of patients who have adverse events.

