### **3.1.2 Dose De-Escalation / Cohort Expansion**

- This trial will begin with a fixed dose of Vicineum 30 mg intravesical (Dose Level 1) administered once weekly for the first 12 weeks. Durvalumab administration will begin after 1 week of Vicineum monotherapy, at 1500mg IV once every 4 weeks.
- In the initial six patients, three subjects at a time will enroll at these doses and schedules (Dose Level 1). Dose-limiting toxicity (DLT) for each subject will be determined during the initial 6-week period that the subject is on treatment (i.e., the DLT period). When all subjects in the initial cohort have been on treatment through the DLT period, all available safety data will be considered in the decision to enroll additional subjects at this dose level, or to de-escalate the doses of the study drugs to Dose Level -1, based on a standard “3 + 3” design (see table below). There will be no dose-escalations in this study.

- After the first six to twelve patients, an additional 18 subjects will be enrolled at the highest dose level at which fewer than 2 of 6 subjects experienced DLT in order to obtain additional safety data and preliminary anti-tumor activity. Treatment at this level will continue as long as the cumulative fraction of patients experiencing DLT is < 1/3.

Dose De-Escalation Schedule	
Dose Level	Dose of IND Agent
Level 1	

• Durvalumab 1500mg IV every 4 weeks

• Vicineum 30 mg intravesically per dose*

Level -1	

• Durvalumab 1500mg IV every 4 weeks

• Vicineum 20 mg intravesically per dose*

\* Vicineum administered weekly during the first 12 weeks of the study, then every 2 weeks thereafter.

Dose de-escalation will follow the rules outlined in the Table below.

If 2 or more DLTs occur at dose level -1, then accrual to the trial will end pending an amendment to consider other dosing options to explore for safety before proceeding to explore efficacy.

Number of Patients with DLT at a Given Dose Level	De-Escalation Decision Rule
0 out of 3	Enter an additional 3 patients at same dose level
1 of 3	

Enter an additional 3 patients at Dose Level 1

• If 0 of these 3 patients experience DLT, enter additional patients at Dose Level 1

• If 1 or more of this group suffer DLT then enter up to 3 patients at the next lowest dose level. Reduce by 1

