## **6 DATA COLLECTION AND EVALUATION**

### **6.1 DATA COLLECTION**

The PI will be responsible for overseeing entry of data into a 21 CFR Part 11-compliant data capture system provided by the NCI CCR and ensuring data accuracy, consistency and timeliness. The principal investigator, associate investigators/research nurses and/or a contracted data manager will assist with the data management efforts. Primary and final analyzed data will have identifiers so that research data can be attributed to an individual human subject participant.

All AEs, including clinically significant abnormal findings on laboratory evaluations, regardless of severity, will be followed until return to baseline or stabilization of event. Document AEs from the first study intervention, Week 1/Day 1, through 90 days after the last administration of the study intervention. After 90 days, only adverse events which are serious and related to the study intervention need to be recorded.

An abnormal laboratory value will be considered an AE if the laboratory abnormality is characterized by any of the following:

- Results in discontinuation from the study
- Is associated with clinical signs or symptoms
- Requires treatment or any other therapeutic intervention
- Is associated with death or another serious adverse event, including hospitalization.
- Is judged by the Investigator to be of significant clinical impact
- If any abnormal laboratory result is considered clinically significant, the investigator will provide details about the action taken with respect to the test drug and about the patient's outcome.

**End of study procedures:** Data will be stored according to HHS, FDA regulations and NIH Intramural Records Retention Schedule as applicable.

**Loss or destruction of data:** Should we become aware that a major breach in our plan to protect subject confidentiality and trial data has occurred, this will be reported expeditiously per requirements in section [7.2.1](#).

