#### **10.4.2 Analysis of the Primary Endpoint**

All patients will be evaluated for the grades of toxicity identified, and the number of patients will DLTs at each dose level will be reported. The MTD will be identified based on being the dose level at which 0 or 1 patient in 6 has a DLT. All toxicities will be tabulated for all 24 or more patients to be enrolled onto the trial.

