#### 14.2.2.2 Phase 2 trial (Study No. VB4-845-02-IIA)

The most commonly reported treatment-emergent adverse events regardless of causality were associated with renal and urinary disorders, including dysuria (60.9% of subjects), hematuria (26.1% of subjects), pollakiuria (23.9% of subjects), micturition urgency (21.7% of subjects), nocturia (15.2% of subjects), incontinence (urge incontinence and urinary incontinence; 13.0% of subjects), urinary tract infections (13.0% of subjects), and bladder pain (10.9% of subjects). Other treatment related AEs that occurred in 10% or more of subjects were fatigue (21.7%), flu-like symptoms (10.9%), fever (10.9%), joint pain (13%), and dizziness (10.9%).

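### The primary endpoint (any adverse event) is not the quantity the 3+3 design acts on, and the MTD sentence rests on six patients with no link to the cumulative one-third DLT rule

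*Combined protocol and SAP*

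**What the plan says.** Section 10.1 says the primary objective is to determine whether the combination "is safe and tolerable as determined by a 3+3 dose de-escalation trial design". The next sentence reads: "The primary endpoint will be the fraction of patients who have adverse events". It gives no grade, attribution, time window or threshold.

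The adverse event definition is wide. Section 8.1.1 counts events "whether or not related to the medicinal (investigational) product". Section 6.1 follows "All AEs, including clinically significant abnormal findings on laboratory evaluations, regardless of severity", and documents them from Week 1/Day 1 "through 90 days after the last administration of the study intervention". Treatment may run to 24 months.

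The 3+3 rules use something else. Section 3.1.1 defines a DLT as a Grade 3 or higher toxicity in the first 6 weeks on treatment, with listed additions and exclusions. Section 3.1.2 adds: "There will be no dose-escalations in this study". Sections 3.1.2 and 10.2 let the 18 expansion patients be treated at the chosen level only while the cumulative DLT fraction stays below 1/3.

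Sections 10.4.2 and 10.4.4 report toxicity grades and the number of patients with DLTs at each dose level. Both then state: "The MTD will be identified based on being the dose level at which 0 or 1 patient in 6 has a DLT". Neither refers to the cumulative rule. Section 10.4.2 also tabulates all toxicities for all 24 or more patients.

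**The concern.** There are two gaps in how the primary objective is answered.

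First, the named endpoint and the decision are different quantities. A fraction that scores Grade 1 dysuria the same as a Grade 4 immune event cannot, by itself, separate a tolerable combination from an intolerable one. The sentence sets no level that would count as acceptable.

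Second, the sentence that names the MTD is satisfied by the six run-in patients, while a separate rule elsewhere uses all patients at that dose. The plan does not say which governs the final dose statement if the two disagree. It plans no interval for the DLT rate, although Section 10.4.3 plans a 95% interval for the response rate, a secondary endpoint. At stake is how firmly a report can state that this dose of the combination is safe.

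**Working it through.** **The plan's own figure.** No sample size, precision or error rate is stated for the primary endpoint. The 24 patients are justified in Section 10.2 by the paired immune-marker tests: 90% power for a 1.0 SD change at two-sided 0.05/25 = 0.002. An exact noncentral-t calculation with n = 24 gives 90.2%, so that figure reproduces. It says nothing about safety.

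**How high the any-AE fraction may be.** No any-AE rate for either drug or the combination appears in the documents.
- Section 14.2.2.2 reports, regardless of causality, urinary events "including dysuria (60.9% of subjects"). If that rate carries over, the any-AE fraction is at least about 61%.
- Section 1.2.1.2 gives adverse events of special interest in 51.9% on durvalumab monotherapy. Assuming independence from dysuria: 1 − (1 − 0.609)(1 − 0.519) = 1 − 0.391 × 0.481 = 0.812.
- If all the listed event terms for both drugs were independent, the figure would be 99.6%.

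The range is therefore about 61% to 99.6%, and every value above 61% needs an independence assumption.

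**Where the two DLT rules disagree.** Inputs: 0 or 1 of 6 (Sections 10.4.2, 10.4.4); cumulative fraction below 1/3, taken here to include the first six (Sections 3.1.2, 10.2).
- 1/6 then 6/18 gives 7/24 = 29.2%. Both rules are met.
- 1/6 then 7/18 gives 8/24 = 33.3%. The cumulative rule fails; the MTD sentence still holds.
- If the rule is checked as patients accrue, 1/6 then 2 of the next 3 gives 3/9 = 33.3%, the same disagreement.

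**Precision (exact Clopper-Pearson 95% intervals).**

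| DLTs / patients | Observed | 95% CI |
|---|---|---|
| 0/6 | 0% | 0-46% |
| 1/6 | 16.7% | 0.4-64% |
| 2/24 | 8.3% | 1-27% |
| 4/24 | 16.7% | 5-37% |
| 7/24 | 29.2% | 13-51% |
| 8/24 | 33.3% | 16-55% |

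**How often a dose is accepted.** With true DLT rate p, P(0-1 of 6) = (1 − p)^6 + 6p(1 − p)^5. At p = 0.30 this is 0.118 + 0.303 = 0.420.

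Adding the cumulative rule only at patient 24 (at most 7 DLTs): 0.1176 × P(X18 ≤ 7) + 0.3025 × P(X18 ≤ 6) = 0.1176 × 0.859 + 0.3025 × 0.722 = 0.319. Checking after each of patients 7 to 24, by exact enumeration, gives 0.246.

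| True DLT rate | Six-patient rule alone | Plus cumulative, checked at 24 only | Plus cumulative, checked after each patient |
|---|---|---|---|
| 30% | 42.0% | 31.9% | 24.6% |
| 40% | 23.3% | 9.6% | 6.5% |

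The documents do not say how often the cumulative fraction is checked, so the last two columns bracket the answer.

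**The case against.** The strongest reply is that the plan is better than its endpoint sentence. Section 10.1 itself says safety is determined by the 3+3 design. Section 10.4.2, the analysis of the primary endpoint, works with grades and DLTs. On this view the any-AE sentence is loose wording, and MTD is simply the run-in label, since Section 2.3.1 describes the expansion as treated at the MTD.

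Much of this stands, and it rules out three stronger readings that a reader might infer.
- *Expansion DLTs are ignored or merely tabulated.* They are not. They govern continued treatment through the one-third rule, and DLT counts per dose level are reported. What is missing is a link to the final dose statement, and an interval.
- *The any-AE fraction will be near 100% whatever the safety.* No document gives such a figure. The floor is about 61%, and only if the phase 2 rate transfers. The phase 3 table in Section 14.2.2.3 shows 50% with any Vicineum-related event, but that counts related events only.
- *A dose with a true 30% or 40% DLT rate is accepted 42% or 23% of the time.* That describes the six-patient sentence alone. With the cumulative rule the figures are about 25-32% and 6-10%.

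The reply does not close the gap. Sections 10.4.2 and 10.4.4 are where the conclusion is drawn, and neither mentions the cumulative rule. A second fair objection is that an exact interval on run-in plus expansion takes no account of selection: with a true 30% rate and a check after each patient, accepted trials show about 21% on average. That calls for a caveat, but 24 patients still inform the rate better than six.

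**Conclusion.** The concern holds in a limited form. The named primary endpoint is unbounded in grade, cause and severity and does not match the DLT decision in the same paragraph. The MTD sentence can be met by a dose that fails the plan's own cumulative rule (8/24 = 33%, CI 16-55%). With no interval planned, a result of 1/6 would be reported without showing that it is compatible with a true DLT rate up to 64%.

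Size: at a true DLT rate of 30%, resting the dose statement on six patients accepts the dose 42% of the time, against 25% to 32% when all 24 count. These figures assume independent patients with a common DLT rate, six run-in plus 18 expansion patients at one level, and a cumulative fraction that includes the run-in. The 61% floor assumes that the phase 2 dysuria rate applies here.

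The term MTD also claims too much if Level 1 passes. Without escalation, that shows only that the highest dose tested was not rejected. The point has less force if Level 1 fails and Level -1 passes.

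**What to change.** In Sections 10.1, 10.4.2 and 10.4.4:

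1. State the primary endpoint as the proportion of patients with a DLT in the 6-week window among all patients treated at the dose carried into expansion (run-in plus expansion), with an exact 95% CI.
2. As a supporting summary, report the proportion with a treatment-related Grade 3 or higher adverse event over all treatment, with an exact 95% CI. This covers toxicity after week 6.
3. Reconcile the MTD sentence with the existing cumulative rule in Sections 3.1.2 and 10.2, so that the final dose statement uses all patients at that dose. State when the cumulative fraction is checked.
4. If Level 1 passes, describe it as the highest dose tested that met the rule.
5. Note that the exact interval is not adjusted for the 3+3 selection and the continuation rule.

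Cost: no new patients or data, since DLTs, grade and relatedness are already recorded. It does need a protocol amendment with IRB approval. Because Section 1.2.3 already reports interim response and tolerability findings, the amendment should say that the change of primary endpoint came after those data were seen. The dose claim becomes more modest.
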